# 12.2.8. Sensitivity Analysis

Sensitivity analyses may be undertaken for the efficacy endpoints in order to evaluate the robustness of the analysis. The following sensitivity analyses may be performed for PFS:

**Progression-Free Survival Sensitivity Analysis 1** (censoring for receiving subsequent systemic anticancer therapy): if a patient is initiated on another anticancer therapy prior to objective progression, including any postdiscontinuation treatment systemic therapy, radiotherapy, or surgical intervention, PFS will be censored at the date of the last complete objective progression-free disease assessment before initiation of the new therapy, regardless of whether or not this patient subsequently had objective progression or died.

**Progression-Free Survival Sensitivity Analysis 2** (nonobjective progression as a PFS event): if a patient is discontinued from study treatment due to investigator determined non-objective progression (for example, symptomatic deterioration), then the patient's PFS time will be calculated using the date of non-objective progression as the progression date.

**Progression-Free Survival Sensitivity Analysis 3** (back-dating progressions at unscheduled assessments): if a patient has objective progression at an unscheduled disease assessment, then the PFS time for that patient will be back-dated to the prior scheduled disease assessment.

Additional sensitivity analyses may be carried out for patients who are *KRAS* positive based only on central test result. Details are described in the SAP.

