**Overall Survival Sensitivity Analysis 2:** A stratified log-rank test with stratification factors the number of prior chemotherapy regimens (1 versus 2), ECOG PS (0 versus 1), and gender (male versus female) from eCRF, and *KRAS* mutation (G12C versus all others) from central lab will be conducted.

The following sensitivity analyses will be performed for PFS:

**Progression-Free Survival Sensitivity Analysis 1** (censoring for receiving subsequent systemic anticancer therapy): if a patient is initiated on another anticancer therapy prior to objective

progression including any postdiscontinuation treatment systemic therapy, PFS will be censored at the date of the last complete objective progression-free disease assessment before initiation of the new therapy, regardless of whether or not this patient subsequently had objective progression or died. The definition of PFS for this sensitivity analyses is presented in Table JPBK.6.2. Those items that differ from Table JPBK.6.1 are underlined.

**Progression-Free Survival Sensitivity Analysis 2** (nonobjective progression as a PFS event): if a patient is discontinued from study treatment due to investigator determined non-objective progression (for example, symptomatic deterioration), then the patient's PFS time will be calculated using the date of non-objective progression as the progression date. The definition of PFS for this sensitivity analyses is presented in Table JPBK.6.3. Those items that differ from Table JPBK.6.1 are underlined.

**Progression-Free Survival Sensitivity Analysis 3** (forward-dating progressions at unscheduled assessments): if a patient has objective progression at an unscheduled disease assessment, then the PFS time for that patient will be forward-dated to the next scheduled disease assessment. The definition of PFS for this sensitivity analyses is presented in Table JPBK.6.4. Those items that differ from Table JPBK.6.1 are underlined.

	Situation	Date of Progression or Censor	Outcome
1	No baseline tumor assessments	Date of Randomization	Censored
2	No post baseline assessments and no death	Date of Randomization	Censored
3	No documented progression and no death (with a post-baseline tumor assessment)	Date of last adequate tumor assessment	Censored
4	Patient lost to follow-up (or withdrew consent from study participation) before documented progression or death	Date of last adequate tumor assessment	Censored

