5	Documented progression	Date of documented progression. If a tumor assessment was done on multiple days, use the earliest date for that visit.	Progressed
6	Death without documented progression	Date of death	Progressed
7	Death or documented progression immediately after missed ≥2 consecutive post-baseline tumor assessment visits	Date of last adequate tumor assessment before missed assessments or date of randomization, whichever is later	Censored
8	New anticancer treatment started	last complete objective progression-free disease assessment before initiation of the new therapy	Censored

#### Table JPBK.6.2. Progression-Free Survival Sensitivity Analysis 1

Note: PFS and associated outcome is determined by the earliest of the dates above, if more than one situation applies

	Situation	Date of Progression or Censor	Outcome
1	No baseline tumor assessments	Date of Randomization	Censored
2	No post baseline assessments and no death	Date of Randomization	Censored
3	No documented progression and no death (with a post-baseline tumor assessment)	Date of last adequate tumor assessment	Censored
4	Patient lost to follow-up (or withdrew consent from study participation) before documented progression or death	Date of last adequate tumor assessment	Censored
5	Documented progression	Date of documented progression. If a tumor assessment was done on multiple days, use the earliest date for that visit.	Progressed
6	Death without documented progression	Date of death	Progressed
7	Death or documented progression immediately after missed ≥2 consecutive post-baseline tumor assessment visits	Date of last adequate tumor assessment before missed assessments or date of randomization, whichever is later	Censored
8	Investigator determined non-objective progression	Date of non-objective progression	Progressed

#### Table JPBK.6.3. Progression-Free Survival Sensitivity Analysis 2

Note: PFS and associated outcome is determined by the earliest of the dates above, if more than one situation applies

#### Table JPBK.6.4. Progression-Free Survival Sensitivity Analysis 3

	Situation	Date of Progression or Censor	Outcome
1	No baseline tumor assessments	Date of Randomization	Censored
2	No post baseline assessments and no death	Date of Randomization	Censored
3	No documented progression and no death (with a post-baseline tumor assessment)	Date of last adequate tumor assessment	Censored

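### Row 8 of SAP Table JPBK.6.2 omits the before-progression condition stated in the SAP text and protocol, so the table read literally censors patients who progress and then switch therapy

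*SAP*

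**What the plan says.** SAP 6.2.10.4 describes PFS Sensitivity Analysis 1 twice.

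- **Text.** Censoring applies "if a patient is initiated on another anticancer therapy prior to objective" progression. The PFS time is then cut at the last clean assessment before the new therapy, "regardless of whether or not this patient subsequently had objective progression or died". Protocol 12.2.8 has the same before-progression condition.
- **Table.** The text adds: "The definition of PFS for this sensitivity analyses is presented in Table JPBK.6.2". Row 8 of that table has the situation "New anticancer treatment started", the date "last complete objective progression-free disease assessment before initiation of the new therapy" and the outcome Censored. It has no condition on the order of therapy and progression. Row 5 still makes documented progression an event, dated as "Date of documented progression. If a tumor assessment was done on multiple days, use the earliest date for that visit".
- **Note under the table.** "PFS and associated outcome is determined by the earliest of the dates above, if more than one situation applies".

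The documents also differ on what counts as new therapy. The protocol's list runs "including any postdiscontinuation treatment systemic therapy, radiotherapy, or surgical intervention". The SAP text names postdiscontinuation systemic therapy only, and row 8 names no type.

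**The concern.** Treatment stops at progression, and long-term follow-up collects subsequent antitumor therapies (Protocol Attachment 1, footnote g). Progression followed by a new therapy is therefore an ordinary sequence in this trial, and the data to trigger row 8 will be there. If row 8 applies to these patients, the analysis censors on something that happens after the event, and removes real progressions. The purpose is the opposite: to see whether switching before progression disturbs the PFS comparison. How much is lost would depend on how many patients in each arm go on to later therapy, which in an open-label trial need not be equal.

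**Working it through.** The plan gives no figure for this analysis, so there is none to reproduce. The check applies the two rules to the same patients and then sizes the difference.

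**1. The rules on example patients.** Scans every 56 days (8 weeks, protocol synopsis), with the baseline scan taken as day 0.

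| Patient | SAP text and protocol 12.2.8 | Table JPBK.6.2 as worded |
|---|---|---|
| Progression day 168, new therapy day 180 | Event, day 168 | Row 5: day 168, event. Row 8: day 112, censored. Earliest date: censored, day 112 |
| New therapy day 130, progression day 168 | Censored, day 112 | Censored, day 112 |
| Progression day 56 (first scan), new therapy day 70 | Event, day 56 | Censored at baseline (day 0) if that scan qualifies; otherwise row 8 has no date and row 5 keeps the event |

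A progression-free scan necessarily precedes the progression scan. So whenever row 8 has a date for a patient who progresses and then switches, the earliest-date note selects it. The two rules agree for switches before progression, the intended cases. The third patient shows a second gap: row 7 falls back on the randomization date, and row 8 does not.

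**2. Size, as an illustration.** Assumptions, none of them the plan's for PFS: 450 patients all followed to an event; exponential times; median time to progression 2.5 months; median survival 6.5 months (the plan's control assumption, used here for everyone); no switch before progression; 30%, 45% or 60% of progressors receiving later therapy.

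- Scan interval: 56 × 12/365 = 1.841 months.
- Progression-free over one interval, ignoring death: 2^(−1.841/2.5) = 0.6002. Alive over one interval: 2^(−1.841/6.5) = 0.8217. Both: 0.6002 × 0.8217 = 0.4932.
- Progression documented at the first scan: 0.8217 × (1 − 0.6002) = 0.3285, or 148 of 450.
- Progression documented at any scan: 0.3285/(1 − 0.4932) = 0.648, or 292 of 450. The other 158 die without documented progression.
- Progression at a later scan: 292 − 148 = 144.

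| Later therapy | Events, text rule | Table, first-scan progressors keep their event: 450 − share × 144 | Table, baseline scan counts: 450 − share × 292 |
|---|---|---|---|
| 30% | 450 | 407 | 362 |
| 45% | 450 | 385 | 319 |
| 60% | 450 | 364 | 275 |

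Simulation of the same scenarios gave 407, 385 and 364 in the first case and 363, 318 and 277 in the second.

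**3. Median PFS.** Under the text rule, the PFS curve just after the first scan is 0.4932, below one half, so the median is the first scan at 1.8 months. If first-scan progressors keep their event, nobody leaves the risk set before that scan, and the median stays at 1.8 months in all three scenarios. If the baseline scan counts, first-scan progressors with later therapy leave at time 0. The curve after the first scan is then 0.4932 × 450/(450 − share × 148), that is 0.547, 0.579 and 0.614. The median passes to a later time; simulation puts it at about 2.6, 3.0 and 3.4 months.

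**The case against.** The strongest defence is that the intended rule is stated twice. The paragraph introducing the table, and protocol 12.2.8, both limit censoring to therapy started before objective progression, and the clause about what "subsequently" happens only makes sense for that order. Row 8 can be read as shorthand for the paragraph above it, and read that way the earliest-date note gives the right answer. This stands in part. It shows which rule was meant, but the SAP calls the table the definition. A programmer also cannot set the note aside, because the same note is what lets row 8 override rows 5 and 6 in the intended cases.

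On size, the SAP does not say that a pre-randomization scan counts as a progression-free assessment. This stands in full: without that reading, the loss of events is roughly halved and the median does not move. The later-therapy shares are also assumed, and the final analysis is planned at about 304 deaths, so not every patient will have been followed to an event.

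On the trigger list, the SAP's wording includes systemic therapy without excluding other types, and protocol 12.2.1 allows the SAP to make minor clarifications. That is fair; it is a mismatch to tidy, not an error in itself.

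**Conclusion.** The table and the text conflict, and the table as worded gives the wrong result for patients who progress and then switch. The scope is one sensitivity analysis of a secondary endpoint. Primary OS and the main PFS analysis (Table JPBK.6.1) are unaffected. On the assumptions shown, a literal reading would take events from 450 to about 407-364, or about 363-275 if the baseline scan qualifies.

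Three stronger readings are not supported.

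- A reader might infer that the plan will delete these events. It will do so only if the table is programmed without regard to the paragraph introducing it.
- A reader might infer a known lengthening of median PFS or a bias in the hazard ratio. The median shift depends entirely on counting the baseline scan, and the documents give no later-therapy rates by arm from which to derive a bias.
- A reader might infer that row 8 misbehaves throughout the sensitivity tables. Row 8 describes a different situation in each. In Table JPBK.6.3, for example, it properly governs when non-objective progression comes before objective progression or death.

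**What to change.** In SAP Table JPBK.6.2:

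1. Extend the row 8 situation so that "New anticancer treatment started" is followed by *before objective progression*.
2. State that row 8 does not apply when documented progression is dated on or before the start of the new therapy, and that otherwise it takes precedence over rows 5 and 6.
3. Add to the row 8 date *or date of randomization, whichever is later*, as in row 7.

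In the SAP text and protocol 12.2.8, use one list of triggering therapies. Keep the protocol's postdiscontinuation qualifier, because palliative radiotherapy is permitted during the study (protocol 9.6.1.1) and should not become a trigger by accident.

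The cost is a few words in one table and one sentence of text. No new data are needed.

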# 10.1. Efficacy Measures

### 10.1.1. Efficacy Assessments at Baseline and during Study Treatment

Imaging studies are performed locally and transmitted for central review.

Baseline tumor measurements will be performed on each patient. Computed tomography (CT), including spiral CT, scans, and magnetic resonance imaging (MRI) are the preferred methods of measurement. Tumor assessments should include the chest and abdominal region. Imaging studies performed  $\leq$ 30 days from date of first dose are permitted as baseline assessment and do not need repeated.

The CT portion of a positron emission tomography (PET)-CT scan may be used as a method of response assessment if the site can document that the CT is of identical diagnostic quality to a diagnostic CT (with intravenous and oral contrast). A PET scan alone or as part of a PET-CT may be performed for additional analyses but cannot be used to assess response according to RECIST.

The method of assessment used at baseline must be used consistently for tumor assessment and must be repeated every other cycle, beginning with Cycle 3 Day 1 until progressive disease is determined. Radiological assessments may be performed up to  $\pm 7$  of the scheduled Day 1 visit. If progressive disease is determined per RECIST Version 1.1 after the start of a new cycle, the patient should be notified and treatment discontinued. If a cycle is delayed, tumor assessment should be concurrent with Day 1 of the new cycle. If the assessment was completed before Day 1 of the next cycle and the patient has a delay in starting the next cycle, the radiological scan does not need to be repeated again when Day 1 of the next cycle is resumed.

For patients continuing treatment after study completion (that is, during the extension phase), efficacy assessments (frequency and type of assessments) will be at the discretion of the investigator, based on the standard of care.

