# 10.1.2. Efficacy Assessments during the Study Period Postdiscontinuation Follow-Up

Postdiscontinuation follow-up during the study period will be conducted as described in the Study Schedule (Attachment 1).

For those patients who discontinue study treatment without objectively measured progressive disease (PD), the investigative sites will continue to monitor patients and periodically evaluate tumor response approximately every 8 weeks by the same method used at baseline until the patient has objective disease progression, or study completion. After the patient has objective disease progression, radiologic tests are no longer required and the patient will be followed up approximately every 60 days ( $\pm$ 14 days) until the patient's death or overall study completion.

Response (CR or PR) should be confirmed before the initiation of additional anticancer therapy. However, initiation of new therapy should not be delayed solely to confirm response.

Efficacy assessments (frequency and type of assessments) for patients still on treatment during the extension phase will be at the discretion of the investigator, based on the standard of care.

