# 10.1.4. Secondary Efficacy Measures

Tumor response is defined by RECIST v1.1 (Eisenhauer et al. 2009) provided in Attachment 5. To derive the overall response rate, a responder is defined as any patient who exhibits a confirmed CR or PR. Best response is determined from the sequence of responses assessed.

A second assessment must be performed  $\geq 28$  days after the first evidence of response. The next scheduled scan at 56 days (8 weeks) would qualify for response confirmation. Two objective status determinations of CR before progression are required for a best response of CR. Two determinations of PR or better before progression, but not qualifying for a CR, are required for a best response of PR. Best response of SD is defined as disease that does not meet the criteria for CR, PR, or PD and has been evaluated at least 1 time, at least 6 weeks after the start of study treatment.

Best response will be derived to encompass all tumor assessments from baseline until the earliest of objective progression or start of new anticancer therapy. Any responses observed after objective progression or the start of new anticancer therapy are excluded from the determination of best response.

Progression-free survival will be defined as the time from randomization until the first evidence of objective progression as defined by RECIST v1.1 (Eisenhauer et al. 2009), or death from any cause, whichever is earlier. Patients who are not known to have either progressed or died at the time of analysis will be censored at the day of their last radiographic tumor assessment, if available, or the date of randomization if no postbaseline radiographic assessment is available. The detailed censoring rules are described in Table JPBK.12.2.

The PFS analysis will be based on the local investigator's tumor assessments.

The date of first documented objective disease progression must be recorded on the CRF even if it occurs after the patient has started a new therapy. Lilly or its designee will collect and store all tumor measurement images on all enrolled patients throughout the study. A central review of imaging scans may be performed by Lilly or its designee.

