4	Patient lost to follow-up (or withdrew consent from study participation) before documented progression or death	Date of last adequate tumor assessment	Censored
5	Documented progression	Date of documented progression. If a tumor assessment was done on multiple days, use the earliest date for that visit.	Progressed
6	Death without documented progression	Date of death	Progressed
7	Death or documented progression immediately after missed ≥2 consecutive post-baseline tumor assessment visits	Date of last adequate tumor assessment before missed assessments or date of randomization, whichever is later	Censored
8	Objective progression at an unscheduled disease assessment	Date of next scheduled disease assessment.	Progressed

Note: PFS and associated outcome is determined by the earliest of the dates above, if more than one situation applies

Additional sensitivity analyses for OS and PFS may be carried out for patients who are *KRAS* positive based only on central test result. Patients who are enrolled with their *KRAS* mutation status based only on local lab reported in the eCRF are excluded in these analyses. For these analyses, the statistical analysis model described in Section 6.2.10.2 will be applied.

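### As written, PFS Sensitivity Analysis 3 reproduces the main PFS analysis and runs opposite to the protocol; the same table note partly defeats Analysis 2

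*SAP*

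**What the plan says.** SAP 6.2.10.4 commits to three PFS sensitivity analyses. Protocol 12.2.8 lists the same three as optional.

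- **Analysis 3, SAP text.** For objective progression at an unscheduled assessment, "the PFS time for that patient will be forward-dated to the next scheduled disease assessment". The text then adds: "The definition of PFS for this sensitivity analyses is presented in Table JPBK.6.4".
- **Analysis 3, Table JPBK.6.4.** Rows 1 to 7 repeat Table JPBK.6.1 (the main PFS rules). Row 5 dates any documented progression on the day it was documented and is not limited to scheduled visits. Row 8 is new, covers progression at an unscheduled assessment, and is dated "Date of next scheduled disease assessment". The note beneath reads "PFS and associated outcome is determined by the earliest of the dates above, if more than one situation applies".
- **Analysis 3, Protocol 12.2.8.** In the same situation, "the PFS time for that patient will be back-dated to the prior scheduled disease assessment".
- **Analysis 2, SAP text and Table JPBK.6.3.** The text makes a non-objective progression that ends treatment a PFS event on its own date. The table adds this as row 8, keeps censoring rows 2, 3, 4 and 7, and carries the same note.

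The SAP Revision History mentions no change of direction for Analysis 3, although Protocol 12.2.1 provides for SAP modifications to be described and justified there.

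**The concern.** The trial is open-label and PFS rests on investigator assessment, so the timing of unscheduled scans is a reasonable thing to test. The SAP gives robustness as the only purpose of these analyses. An analysis that must equal the main result whatever the data cannot supply evidence of robustness, yet its agreement could be reported as if it did.

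The table, the SAP text and the protocol also give three different dates for the same patient, so the result depends on which one the programmer follows. In Analysis 2, the patients left censored are among those whom the analysis is meant to turn into events.

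**Working it through.** The plan gives no figure on this point, so the check applies the rules as written. Days are counted from randomization. For illustration, first dose is on the same day and no cycle is delayed.

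**1. Table JPBK.6.4 against Table JPBK.6.1.** Let u be the date of an unscheduled progression, n the next scheduled assessment (n > u), and r the earliest date from any other row that applies.

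- Table JPBK.6.1: min(u, r).
- Table JPBK.6.4: min(u, n, r) = min(u, r), because n > u.

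A patient without an unscheduled progression never meets row 8. The two tables therefore agree in date and outcome for every patient. Coding both and applying them to 200,000 simulated patients, at assumed unscheduled-scan probabilities of 10%, 20% and 40%, gave 0 differences each time. The identity does not depend on those assumptions.

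**2. Three sources, one patient.** The scan interval is 8 weeks (Protocol 10.1.4: "The next scheduled scan at 56 days (8 weeks) would qualify for response confirmation"). Scans are due at days 56 and 112, and unscheduled progression is documented at day 70.

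| Source | PFS event date |
|---|---|
| Main analysis (Table JPBK.6.1) | 70 |
| Table JPBK.6.4 with its note: min(70, 112) | 70 |
| SAP text (forward) | 112 |
| Protocol 12.2.8 (backward) | 56 |

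**3. Size of the date shift on an undelayed schedule.** Take scans at days 56, 112, ..., 336 and treat days within 7 of a scan as scheduled. That removes 5 × 15 + 8 = 83 of 336 days and leaves 253 unscheduled days.

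- Table as written: 0 of 253 change.
- SAP text: all 253 move later, by 8 to 55 days (mean 28.7).
- Protocol: all 253 move earlier, by 1 to 48 days (mean 27.3).

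The mean shifts add to one interval, 28.7 + 27.3 = 56 days. These are counts of possible days, not patient frequencies.

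**4. Table JPBK.6.3 under the same note.**

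| Course | Competing row and date | Row 8 date | Result |
|---|---|---|---|
| No post-baseline scan, deterioration day 40, alive | Row 2, day 0 | 40 | Censored day 0 |
| Last scan 56, deterioration 75, alive, no later scan | Row 3, day 56 | 75 | Censored day 56 |
| Last scan 56, deterioration 75, then lost | Row 4, day 56 | 75 | Censored day 56 |
| Last scan 56, deterioration 75, scans 112 and 168 missed, death 200 | Row 7, day 56 | 75 | Censored day 56 |
| Deterioration 75, objective progression 112 | Row 5, day 112 | 75 | Event day 75 |
| Deterioration 75, death 100 | Row 6, day 100 | 75 | Event day 75 |
| Deterioration 75, progression-free scan 112, alive | Row 3, day 112 | 75 | Event day 75 |

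The first four results contradict the SAP text for Analysis 2 and the last three agree with it. These are illustrative courses, not proportions.

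**5. The scheduled date.** After an unscheduled progression the next scan will usually not take place: "After the patient has objective disease progression, radiologic tests are no longer required" (Protocol 10.1.2). During treatment the schedule also moves: "If a cycle is delayed, tumor assessment should be concurrent with Day 1 of the new cycle" (Protocol 10.1.1). The SAP does not say that the date comes from the planned schedule whether or not the scan is done.

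**The case against.** The strongest reply is that the intent for Analysis 3 is plain. The SAP text says forward-dating in both the label and the sentence, and it says items that differ from Table JPBK.6.1 are underlined. The underlining, not visible in the text reviewed, would mark row 8 as the intended change. The note looks carried over from Table JPBK.6.1, and a programmer reading text and table together might well let row 8 replace row 5.

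That answers what the authors probably meant, but not what they specified. The text names the table as the definition, row 5 is worded exactly as in Table JPBK.6.1, and nothing says row 8 replaces it. Nor does it help with the protocol, which points the other way in current text.

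Two further replies stand in part. Protocol 10.1.1 and 10.1.2 do supply a schedule, so the next date can be derived once the SAP refers to it. Protocol 10.1.2 also requires scans to continue about every 8 weeks after discontinuation without objective progression. When they are done, row 8 of Table JPBK.6.3 works, so failures arise mainly with missed scans, loss to follow-up or an early cutoff. Study Schedule footnote f, which ends imaging at the next line of treatment, pulls the other way.

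A reader might infer three stronger points that the documents do not support:

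- **That Analysis 2 fails altogether.** It does not, as the last three courses in the working show.
- **That the SAP and protocol dates always lie 56 days apart.** This holds only without delays. With a scan at day 56 and one 14-day cycle delay, the next is due at 56 + 56 + 14 = day 126, a gap of 70 days. Before the first scan the gap also depends on the time from randomization to first dose.
- **That the PFS hazard ratio is materially distorted.** The frequency of unscheduled or non-objective progressions in each arm is not given, so no size can be derived.

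**Conclusion.** The point holds as a minor error in the plan as written. Table JPBK.6.4 with its note changes no patient's date or outcome from the main PFS analysis. This follows from the wording alone and rests on no assumption about the data. The conflict of direction between SAP 6.2.10.4 and Protocol 12.2.8 is equally clear; on an undelayed 8-week schedule the two differ by one full scan interval.

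The defect in Table JPBK.6.3 is partial. It affects patients for whom row 2, 3, 4 or 7 gives a date before the non-objective progression.

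Only sensitivity analyses of a secondary endpoint are involved. The OS test and the main PFS definition are unaffected.

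**What to change.** **Direction.** State one direction for Analysis 3, with the reason, in both documents.

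- *If forward-dating:* limit row 5 of Table JPBK.6.4 to progression at scheduled assessments, or state that row 8 replaces row 5. Date row 8 to the next planned assessment, or to death if earlier. Say what applies when that date falls after the data cutoff.
- *If back-dating:* set row 8 to the prior scheduled assessment, no earlier than randomization. The existing note then works unchanged.

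**Scheduled date.** Take it from the protocol's own schedule, whether or not the scan was done. On treatment this is the first day of alternate cycles from Cycle 3, within 7 days either side, moving with cycle delays. After discontinuation it is about every 8 weeks. Do not use a fixed 56-day grid on treatment. In the delayed example above, such a grid would plan day 112 (window 105 to 119) and class the required day 126 scan as unscheduled.

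**Table JPBK.6.3.** State that row 8 takes precedence over rows 2, 3 and 4, and over row 7 where the missed visits follow the non-objective progression. Against rows 5 and 6 the earliest date stands.

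**Cost.** A few words in two SAP tables, a sentence on direction in each document, and minor programming before database lock. If the lock has passed, SAP 6.2.1 provides for describing and justifying the change in the clinical study report.
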